7.3 Planned Interim Reports

Interim reports may be generated during the course of the study. The reports will only be made available to the Sponsor team and Click Diagnostics for the purpose of submission to the FDA. The study operators and laboratory staff that run the assays will not have access to the reports. The study statistician will provide the reports, which will contain summaries from analyses outlined in section 7.4 and detailed in the separate Statistical Analysis Plan.

The reports will be generated after the data are entered in the database; the approximate milestones for the generation of each report are provided in Table 5 below:

Table 5. Types of Study Reports and Schedule

Report Type	Milestone
Interim Report ¹	After the collection of 50 PIS-positive CT samples, 50 PIS-positive TV samples, 20 PIS-positive prospectively collected NG samples
510(k) Report	After the collection of 100 PIS-positive CT samples, 100 PIS-positive TV samples, ≥45 PIS-positive prospectively collected NG samples
CLIA Waiver Report	After the collection of 120 PIS-positive CT samples, 120 PIS-positive TV samples, ≥45 PIS-positive prospectively collected NG samples

¹The need for this interim report depends on the rate of enrollment of subjects with PIS-positive NG samples. The report will be generated if it is possible to do so without halting enrollment and/or losing momentum in accrual or if the rate of enrollment of subjects who are PIS-positive NG is such it is expected that multiple NG milestones will not be met in a short period of time.

It is not anticipated that the study or its operations will be impacted by the analyses performed for the interim report (e.g., early termination of the study), but instead the report fulfills a regulatory requirement and provides the FDA an update on the progress of the trial. As such, adjustments for the multiple interim calculations of interval estimates are not planned.

The 510(k) and CLIA Waiver reports will be generated once the NG enrollment has finished per the enrollment procedure outlined in section 7.2. Though it is possible that NG sensitivity will be estimated multiple times, no adjustments for the multiple calculations are planned.

7.3.1 Ongoing Investigative Product Performance Tracking

The primary analysis of agreement of Click Sexual Health Test results compared to PIS will be performed as described in section 7.4.3 and as shown in the example 2 x 2 contingency table depicted in Figure 6 of this protocol on an ongoing basis during the course of the study. These analyses will track performance of the investigative device and thereby serve to inform the Sponsor team and Click Diagnostics as to the likelihood of successful completion of the study with performance conforming to acceptance criteria, or conversely, to eventual futility of the study for failure to achieve acceptable performance. In no case shall the results of these ongoing analyses initiate an early termination of the study for

benefit, i.e. based upon early achievement of acceptable performance.

In accord with DMID Policy, analysis results shall be distributed only to the Sponsor team and to Click Diagnostics and the receiving personnel shall not further distribute the results. No results shall be supplied to study site personnel or to study monitors, and neither the raw data nor the analysis of these ongoing analyses shall be submitted to FDA. Study updates will only be provided to the FDA at timepoints listed in Table 5 above. The results of these ongoing analyses shall not translate into study design changes, protocol amendments, or investigative device design changes. As such, no adjustments for the multiple analysis will be made.

7.4 Analysis Plan

A separate statistical analysis plan document will be generated that will contain the details of all interim and final analyses. This section outlines the major components of all analyses.

7.4.1 Analysis Populations

The following analysis populations will be defined separately for each report (Interim, 510(k), CLIA Waiver). The statistical analysis plan will include the further details on the definitions of the report-specific analysis populations.

Enrolled Population: This population includes all participants enrolled at the time of the data cut-off for the report.

Evaluable Population: This population includes all samples available at the time of the data cut-off for the report, which provide an evaluable Click Diagnostics Sexual Health Test result and an evaluable PIS result for each tested pathogen (CT, NG, TV). There will be a separate Evaluable population for each organism.

A sample provides an evaluable result if both the Click device and the PIS provide a valid positive or negative result.

The primary outcome measure of sensitivity and specificity of the Click Diagnostics Sexual Health Test will be evaluated in the evaluable population.

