Recruitment goals for the 510(k) phase of the study are at least 100 specimens positive for CT, 100 specimens positive for TV, and 45 specimens positive for NG as determined by PIS. Recruitment goals for the CLIA waiver phase of the study are 120 positive specimens for CT and TV (prospective), and 45 positive specimens for NG. In order to achieve the required precision for sensitivity of NG detection, additional specimens may be required. Banked NG positive specimens may also be used and will be provided to the testing sites for Click device testing. Thus, the maximum target for the number of PIS-positive NG samples is 85. At specified enrollment targets, the sensitivity of the Click device with respect to NG will be estimated. If the NG estimate meets the requirements for the 510(k) and CLIA waiver phases at any of the interim points and the enrollment targets for CT and TV have been met, collection of samples will stop. Otherwise, collection of samples will continue. See section 7 for details on the interim reviews. At least 30% of total samples must be from sites considered low prevalence. All comparator tests will be performed by a reference laboratory.

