5.4.2 Exclusion Criteria

1. Previously enrolled in this study.

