7.2 Sample Size Considerations

Recruitment goals for the 510(k) phase of the study are at least 100 specimens positive for each of CT and TV, and at least 45 specimens positive for NG, as determined by PIS. Recruitment goals for the CLIA waiver phase of the study are 120 positive specimens for each of CT, TV, and 45 NG. Approximately 585 subjects will be recruited from low-prevalence sites (one third of the 1,750) and approximately 1165 subjects will be recruited from high prevalence sites. The average expected proportion of samples positive via PIS for CT, TV, and NG among subjects enrolled at the high prevalence sites are, respectively, 12.4%, 19.5%, and 8.1%. The corresponding estimates for the low-prevalence sites are 1.7%, 1.0%, and 1.4%. Based on these prevalence estimates, it is expected that the enrollment targets will be met for the three organisms. Thus, the study as designed is expected to meet the 510(k) and CLIA waiver recruitment goals for all three organisms. If NG prevalence is lower than expected, banked NG+ samples may need to be leveraged to meet the recruitment goals for NG. As indeterminate PIS results or invalid or failed Click device results are expected for a small number of cases, enrollment may extend beyond 1750 to replace these results. The duration of enrollment may be extended if the actual prevalence of any of the organisms is lower than predicted.

For the estimation of the sensitivity and specificity of the Click device, we assume both the sensitivity and specificity is at least 95%. For 510(k) clearance, the study aims to demonstrate that sensitivity to each of CT and NG is at least 95%, with a lower bound of the two-sided 95% Wilson Score confidence intervals at least 90%, and to demonstrate that sensitivity to TV is at least 95%, with a lower bound of the two-sided 95% Wilson Score confidence intervals at least 85%. Regarding specificity, the study aims to demonstrate specificity to each of CT, TV, and NG is at least 95%, with a lower bound of the two-sided 95% Wilson Score confidence intervals at least 90%. For the CLIA waiver, the study aims to demonstrate that both the sensitivity and specificity to each of CT, TV, and NG is at least 95%, with a lower bound of the two-sided 95% Wilson Score confidence intervals at least 89%.

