7.4.3 Primary and Secondary Analyses

Sample proportions of subjects who are PIS-positive for each of the three organisms among all enrolled subjects and by symptomatic status will be estimated overall and by clinical site. Point estimates and 95% Wilson Score confidence intervals will be generated.

Table 6 below presents a 2 x 2 contingency table displaying the potential performance outcomes for the Click device in comparison to PIS, Where TP = Number of True Positives, TN = Number of True Negatives, FP = Number of False Positives, and FN = Number of False Negatives.

Table 6: 2 x 2 Contingency Table for Click Diagnostics versus PIS

		PIS	
		Infected	Not Infected
Click Diagnostics Sexual Health Test	Infected	TP	FP
	Not Infected	FN	TN

Sensitivity, specificity, positive predicted value (PPV), and negative predicted value (NPV) will be estimated along with their 95% Wilson Score confidence interval. The following formulae will be used to estimate the performance characteristics:

- Sensitivity (%) = $TP/(TP + FN) * 100$
- Specificity (%) = $TN/(TN + FP) * 100$
- PPV (%) = $TP/(TP + FP) * 100$
- NPV (%) = $TN/(TN + FN) * 100$

The above estimates, along with the number of true/false positives/negatives, will be calculated overall, by clinical site, and by symptomatic status. Subject listings of test results will be generated.

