6.2.2. Evaluable Population

The Evaluable analysis population will include all subjects enrolled with a valid Click result and a valid PIS designation. There will be a separate Evaluable population for each organism. A subject will be excluded from the organism-specific evaluable population if any of the following criteria are met:

- Either the Click result is invalid or the PIS designation is indeterminate
- The specimen for either the Click or comparator assays is missing or untested
- The specimen for the Click device was tested more than 2 hours after collection
- The specimen for the comparator assay was tested outside the stability window
- Subject did not meet eligibility criteria
- Any protocol deviation that, in the opinion of the investigators, is deemed to impact validity of assay results
- Any other reason that, in the opinion of the investigators, is deemed to impact validity of assay results (e.g. receipt of a concomitant medication that could interfere with assay results)

See Section [3.3.2](#) for definitions of valid result and designation.

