8.3. Analysis of the Exploratory Outcomes

[Table 36](#) and [Table 37](#) will present summaries of responses to individual items on the Operator ease of use questionnaire. For each item on the questionnaire, the proportion of study operators who select each level of

the response will be provided as well as the distribution of each item's responses (e.g., mean, standard deviation, median, range). [Listing 13](#) will provide a listing of individual operator responses.

For the exploratory outcome measure of prevalence of each organism (as determined by PIS or the Click device), the overall, by site, and by symptomatic status estimates will be contained in the primary and secondary analysis contingency tables described above.

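### The protocol and SAP disagree on where banked NG-positive specimens are analysed: one pools them into NG PPV and NPV, the other, read literally, drops them even from NG sensitivity

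*Protocol*

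**What the plan says.** **Use of banked specimens.** Protocol section 4: "Banked NG positive specimens may also be used and will be provided to the testing sites for Click device testing". Protocol 7.2 gives the trigger: "If NG prevalence is lower than expected, banked NG+ samples may need to be leveraged to meet the recruitment goals for NG". The maximum is 85 PIS-positive NG samples. SAP 4.1, 4.2 and 5 repeat these provisions. Protocol 5.4.2 lists one exclusion for banked donors: "Previously enrolled in this study".

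**Protocol analysis set.** Protocol 7.4.1, on the Evaluable population: "This population includes all samples available at the time of the data cut-off for the report", given an evaluable Click and PIS result. It sets no prospective-only limit and leaves further detail to the SAP. Protocol 7.4.3 then builds one 2x2 table: "Sensitivity, specificity, positive predicted value (PPV), and negative predicted value (NPV) will be estimated along with their 95% Wilson Score confidence interval". These are reported overall, by site and by symptomatic status. The same section estimates the PIS-positive proportion among enrolled subjects.

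**SAP analysis set.** SAP 6.2.2: "The Evaluable analysis population will include all subjects enrolled with a valid Click result and a valid PIS designation". One of its exclusions is: "The specimen for the Click device was tested more than 2 hours after collection". SAP 8.1.1 takes sensitivity, specificity, accuracy, PPV and NPV from Table 22, whose denominator is this population. For prevalence, SAP 8.3 says "the overall, by site, and by symptomatic status estimates will be contained in the primary and secondary analysis contingency tables described above". SAP section 12 states that its analyses coincide with the protocol's.

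**The concern.** Sensitivity is calculated within infected specimens, so known positives can inform it if they are otherwise comparable. PPV, NPV, accuracy and prevalence depend on the mix of infected and uninfected. Adding positives with no matching uninfected women changes that mix by choice of the study team, and the resulting PPV describes no population.

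The two documents leave two outcomes open, and neither is satisfactory. Under the protocol's wording, NG PPV carries an ordinary Wilson interval but depends partly on how many vials were tested, and by-site PPV depends on which sites received them. Under the SAP's wording, banked specimens count toward the NG target but belong to no analysis population, so they cannot improve the precision of NG sensitivity, which is why they are allowed. The choice would also be made by people who already see results: Protocol 7.3.1 sends ongoing performance analyses to the sponsor team and the manufacturer.

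**Working it through.** **1. The plan's own figures.** The documents state no NG PPV. They give lower Wilson bounds for NG sensitivity (Protocol Table 4) and say that the enrolment targets should be met (Protocol 7.2).
- Recalculating the Table 4 bounds matches 14 of 15 to one decimal. The other, 55 positives with 3 false negatives, comes to 85.1% against a stated 85.2%, a rounding difference.
- Expected NG positives from Protocol 7.2: 1165 × 0.081 + 585 × 0.014 = 94.4 + 8.2 = 102.6. This exceeds both the minimum of 45 and the maximum of 85.
- Prevalence would have to fall below 45/102.6 = 44% of plan to miss 45, or below 85/102.6 = 83% of plan to miss 85.

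**2. How many banked specimens.** Protocol Table 5 sets at least 45 prospectively collected NG positives as the milestone for the 510(k) and CLIA waiver reports. With a maximum of 85, at most 85 − 45 = 40 can be banked.

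**3. Does a banked vial enter the table?**

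| Rule | Banked vial |
|---|---|
| Protocol 7.4.1, sample-based | In, if Click and PIS results are valid |
| SAP 6.2.2, enrolled subjects | Out: the donor must not have been enrolled |
| SAP 6.2.2, 2-hour rule | Out: the specimen was frozen and tested later |
| SAP 3.3.4 to 3.3.8, TP, FP, TN and FN counted as specimens | Does not settle it |

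**4. Effect if pooled.** Assumptions not in the documents: 1,750 prospective evaluable women, 45 NG-positive (so 1,705 negative), b = 40 banked positives, sensitivity 95% in both sources, and specificity from 95% to 99%. (Protocol 7.2 assumes at least 95% for each.)

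- PPV = 0.95(45 + b) / [0.95(45 + b) + (1 − spec) × 1705]
- NPV = spec × 1705 / [spec × 1705 + 0.05(45 + b)]

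True positives are 0.95 × 45 = 42.75 without banked specimens and 0.95 × 85 = 80.75 with 40.

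| Specificity | False positives | PPV, prospective only | PPV, with 40 banked |
|---|---|---|---|
| 95% | 85.25 | 42.75/128.00 = 33.4% | 80.75/166.00 = 48.6% |
| 98% | 34.10 | 42.75/76.85 = 55.6% | 80.75/114.85 = 70.3% |
| 99% | 17.05 | 42.75/59.80 = 71.5% | 80.75/97.80 = 82.6% |

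At specificity 95%, NPV goes from 1619.75/1622.00 = 99.86% to 1619.75/1624.00 = 99.74%. Specificity does not change, because no negatives are added. Accuracy hardly moves: at specificity 99% it is 1730.70/1750 = 98.9% before and 1768.70/1790 = 98.8% after. With fewer vials the PPV shift is smaller: 10 banked gives 38.0% at specificity 95% and 75.4% at 99%.

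**5. One vial at a time.** Take 43 true positives, 2 false negatives and 85 false positives. A Click-positive vial moves PPV from 43/128 = 33.59% to 44/129 = 34.11%. A Click-negative vial leaves PPV at 33.59% and lowers NPV from 1620/1622 = 99.88% to 1620/1623 = 99.82%. The rise in PPV is therefore an expectation, not a certainty for each specimen.

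**6. Prevalence.** The protocol's estimate is among enrolled subjects, so banked donors are not in it. If vials were placed in the SAP tables, table-based prevalence would go from 45/1750 = 2.57% to 85/1790 = 4.75%.

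**The case against.** The strongest reply is that the protocol defers population details to the SAP, and the SAP keeps banked vials out. Its table shells agree: Tables 4 and 5 start from enrolled subjects, and Table 22 uses the Evaluable population. A reader might infer that banked positives definitely enter Tables 22 and 31 to 35; the SAP text does not support that. But the exclusion follows from general rules, not from a stated decision about banked specimens. The SAP still counts those specimens toward the NG target, gives them no table, and claims to coincide with a protocol whose population is defined by samples. The conflict therefore stands.

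A reader might also infer that reported NG prevalence is inflated. It is not under the protocol's enrolled-subject estimate, nor under SAP 6.2.2 read literally; inflation needs the protocol's sample set inside the SAP's tables, a combination neither document specifies. Nor may one assume that most of the 85 could be banked: Table 5's minimum of 45 prospective positives stands against that, although Protocol 7.2 lets banked samples help meet the NG goal.

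Three further points limit the concern. Banked use is optional and tied to low prevalence. PPV is not among the primary or secondary endpoints, and even the prospective figure reflects a designed mix of low- and high-prevalence sites. SAP Table 29 gives PPV and NPV at fixed prevalences, free of the sample mix. All three stand, but PPV is still reported with the primary analysis in Table 22.

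**Conclusion.** The point holds as a conflict between the two documents with a conditional consequence. As written, banked NG specimens either distort NG PPV and slightly lower NPV (protocol wording), or are lost from the sensitivity estimate they are meant to support (SAP wording). If they are pooled at the largest number consistent with Table 5, NG PPV rises by about 11 to 15 percentage points across specificities of 95% to 99%, while NPV falls by about 0.1 point. This rests on the illustrative 45 + 40 split, 1,750 prospective evaluable women and equal sensitivity of 95% in both sources. Specificity and the protocol's prevalence estimate are unaffected. At the planning prevalences the situation would not arise, since about 103 NG positives are expected. It deserves a rule now because banked use is expressly permitted and the rule is easy to set before any such specimens are analysed.

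**What to change.** Reconcile Protocol 7.4.1 and 7.4.3 with SAP 6.2.2, 8.1.1, 8.2 and 8.3:

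- State that NG PPV, NPV, accuracy and prevalence (SAP Tables 22 and 31 to 35) use prospectively enrolled subjects only.
- State that banked specimens, if used, contribute to NG sensitivity only. Give them an explicit SAP population rule that says how the enrolled-subject and 2-hour criteria apply to them.
- Show prospective and banked counts and sensitivities separately and combined.
- Add a specimen-source flag to the analysis dataset.

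The cost is a few sentences in each document, one variable and extra rows in the NG tables. If banked specimens are never used, nothing else changes. If they are, the reported NG PPV will be less favourable than the pooled figure.

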7.4.2 Baseline Characteristics and Subject Disposition

Baseline and demographic characteristics and subject disposition, including but not limited to the number of subjects who contributed vaginal swabs and reasons for withdrawn samples, will be summarized overall and by clinical site. For both continuous and categorical variables, appropriate summary statistics will be applied. For continuous variables, descriptive statistics will include the number of non-missing values, mean, standard deviation, median, minimum, and maximum. For categorical variables, descriptive statistics will include counts and percentages per category.

7.4.3 Primary and Secondary Analyses

Sample proportions of subjects who are PIS-positive for each of the three organisms among all enrolled subjects and by symptomatic status will be estimated overall and by clinical site. Point estimates and 95% Wilson Score confidence intervals will be generated.

Table 6 below presents a 2 x 2 contingency table displaying the potential performance outcomes for the Click device in comparison to PIS, Where TP = Number of True Positives, TN = Number of True Negatives, FP = Number of False Positives, and FN = Number of False Negatives.

Table 6: 2 x 2 Contingency Table for Click Diagnostics versus PIS

		PIS	
		Infected	Not Infected
Click Diagnostics Sexual Health Test	Infected	TP	FP
	Not Infected	FN	TN

Sensitivity, specificity, positive predicted value (PPV), and negative predicted value (NPV) will be estimated along with their 95% Wilson Score confidence interval. The following formulae will be used to estimate the performance characteristics:

- Sensitivity (%) = $TP/(TP + FN) * 100$
- Specificity (%) = $TN/(TN + FP) * 100$
- PPV (%) = $TP/(TP + FP) * 100$
- NPV (%) = $TN/(TN + FN) * 100$

The above estimates, along with the number of true/false positives/negatives, will be calculated overall, by clinical site, and by symptomatic status. Subject listings of test results will be generated.

7.4.4 Exploratory, Ancillary, and Other Analyses

Responses to individual items on the Ease-of-use questionnaire will be summarized. For each item on the questionnaire, the proportion of study operators who select each level of the response will be summarized. In addition, the distribution of each item's responses (e.g., mean, standard deviation, median, range) will be calculated.

Multiple ancillary analyses, which support the primary and secondary analyses, will be performed and included in the interim and final reports. The statistical analysis plan will include full details of the planned analyses; below are high-level summaries of the analyses.

The number of invalid or missing results from and failed tests of the Click device will be summarized overall and by clinical site. The different combinations of results among the PIS assays will be tabulated overall, by organism, and by symptomatic status.

Using the observed sensitivity and specificity of the Click device, hypothetical PPV and NPV values will be calculated across a range of hypothetical prevalence rates given the following formulae:

- $PPV = sens * p / [Sens * p - (1 - spec)*(1 - p)] * 100$
- $NPV = spec * (1 - p) / [(1 - sens) * p - spec*(1 - p)] * 100$

Where Sens = Sensitivity, Spec = Specificity, and p = prevalence.

Additional supplemental and exploratory analyses, including sensitivity analyses, which assess the impact of indeterminate/invalid/failed/missing results on the analyses, may be performed and will be specified in the statistical analysis plan.

